9.2.1 Treatment Assignment Procedures

Eligible individuals who consent to participate will be randomly assigned to one of 16 study conditions (Table 3). Our study statistician who has no contact with study participants and will have no access to outcome data until database lock, will create randomization tables using Microsoft Excel and upload to our data collection system (REDCap) prior to the start of recruitment for Phase 1. Because this is a 16-cell design, we will not stratify by any variables at baseline. Block size is effectively 12 (i.e., number of participants per cell.)

Study staff will not have access to randomization tables. When a person is deemed eligible, study staff will verify the stratification variables in REDCap and then click the “RANDOMIZE” button.

For Phase 1, given there are few participants, we want to ensure that each site has an opportunity to pilot each intervention component and certain key combinations.

Table 3. Balanced Factorial Design Assessing Four Candidate Intervention Components

Cell	COMPONENT				Phase 1	Phase 2
	1	2	3	4	n	n
1	No	No	No	No	1	12
2	No	No	No	Yes	1	12
3	No	No	Yes	No	1	12
4	No	No	Yes	Yes	1	12
5	No	Yes	No	No	1	12
6	No	Yes	No	Yes	1	12
7	No	Yes	Yes	No	1	12
8	No	Yes	Yes	Yes	2	12
9	Yes	No	No	No	1	12
10	Yes	No	No	Yes	1	12
11	Yes	No	Yes	No	1	12
12	Yes	No	Yes	Yes	2	12
13	Yes	Yes	No	No	1	12
14	Yes	Yes	No	Yes	1	12
15	Yes	Yes	Yes	No	2	12
16	Yes	Yes	Yes	Yes	2	12

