1. STUDY OBJECTIVES

1.1 Primary Objective

Our project will have two phases. Specific aims for each phase are:

Phase 1 – MOST Preparation Phase:

1. To conduct a pilot trial at two new OAT clinic sites, enrolling n=10 at both sites, for a total n=20.
2. Establish clinical trial procedures and document feasibility at both sites prior to conducting a fully powered optimization trial.
3. Demonstrate our ability to a) recruit participants; b) train yoga teachers to fidelity; c) randomize participants to intervention components and correctly administer components; d) run classes; and e) collect follow-up assessments.

Phase 2 – MOST Optimization Phase:

4. To conduct a factorial experiment that will allow us to evaluate the impact of each of the 4 intervention components on yoga dosage received. We will enroll a total n=192. All participants will receive the core yoga intervention, with random assignment to the four intervention components outlined above.
5. Use results from Phase 2 to choose an efficient combination of intervention components that, together with standard yoga classes, maximizes yoga dosage.
6. Examine mechanisms by which components are hypothesized to work.

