A member of the research staff will also sign the consent form (either on paper or electronically). After informed consent is obtained, participants will then be evaluated using the baseline diagnostic and assessment measures to confirm eligibility. Consent forms will be stored in a secure location at Butler Hospital (for patients recruited at CODAC) or Boston Medical Center, or be located in REDCap. Participants will be given a copy of the consent form to keep.

Enrollment and Randomization

Enrollment procedures are identical for Phase 1 and Phase 2.

Randomization will occur after participants are deemed eligible. To be eligible after consent participants must: 1) have completed the baseline assessments and passed inclusion criteria, and 2) confirmed their interest.

All participants receive the standard yoga intervention, and are randomized to receive or not receive four intervention components. Each participant will be randomized to one of 16 study groups. Participants are considered “enrolled” after randomization.

Once enrolled, a participant will receive a) a study cell phone with a data plan; b) a yoga mat and two blocks; and c) a booklet describing basic yoga practices and ways to more safely engage in yoga. The study cell phone will be used for assessment phone calls, study classes via a secure video-based platform, and to administer some study intervention components. Once a participant receives the phone, a study staff member will call them to give the participant any guidance that they need regarding how to use the phone for study-related activities. During the course of the study, participants will not be restricted from using the phone for other activities. Participants will be asked to return the phone at the end of study participation.

Documentation of Reasons for Ineligibility

All participants who express interest in the study will be tracked in a separate database along with the status of their participation. Any participant who is screened for any aspect of the study including Phase 1 or Phase 2 (even if only one inclusion criterion is assessed before the participant is determined not eligible) will have a study record documenting which inclusion criteria were assessed and the outcome of that assessment (i.e., as part of a study log).

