9.5 Outcomes

9.5.1 Primary/Proximal Outcome

Phase 1 is a pilot study to assess feasibility. The primary aims and outcome assessments are shown in Table 4 below.

Table 4. Targets for Phase 1 Pilot Study.		
Feasibility Area	Method of assessment	Target at each site
Recruit participants	Number recruited per month	Recruit 10 participants in 4 months.

Train yoga teachers to fidelity	Teacher fidelity scale	Each teacher demonstrates >80% fidelity on final 3 classes rated.
Randomize participants to intervention components and correctly administer these components	Randomization errors; receipt of incorrect intervention components	No errors/ incorrect components received in 2 nd half of participants randomized.
Collect follow-up assessments	Percent of follow-up assessments collected (for M1, M2, and M3)	≥ 70% with sufficient data collected on dosage; ≥ 70% of other follow-up assessments collected, including chart reviews

The proximal outcome of Phase 2 is yoga dosage received. This will be calculated by adding total number of minutes per week in the study yoga class and total number of minutes per week in personal practice (or outside yoga classes). Research staff will take attendance at study yoga classes, and, in the event someone does not attend the entire yoga class, will record the number of minutes present in class. We will measure personal practice using the Weekly Personal practice Questionnaire.

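### Do the loose stratification and block-size wording and the undescribed Phase 1 site allocation in section 9.2.1 call for a change to the randomization?

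*Combined protocol and SAP*

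**What the plan says.** Section 9.2.1 describes the allocation in three short paragraphs and Table 3.

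- On stratification: "Because this is a 16-cell design, we will not stratify by any variables at baseline". In the next paragraph, before randomizing, "study staff will verify the stratification variables in REDCap". No such variable is named there or elsewhere. Section 9.6 lists site, sex, age and OAT type, but as analysis covariates.
- On blocking: "Block size is effectively 12 (i.e., number of participants per cell)".
- On Phase 1: "we want to ensure that each site has an opportunity to pilot each intervention component and certain key combinations". Table 3 gives one Phase 1 count per cell for both sites together. Cells 8, 12, 15 and 16 have two participants and the other twelve cells have one.

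Section 4.3 adds that "Enrollment procedures are identical for Phase 1 and Phase 2" and "Each participant will be randomized to one of 16 study groups". Section 1.1 sets the Phase 1 size: "enrolling n=10 at both sites, for a total n=20". The recruitment target for each site in Table 4 (section 9.5.1) is "Recruit 10 participants in 4 months".

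**The concern.** Read literally, staff are told to check variables that the design says do not exist. A reader cannot tell whether site is a stratum. The number given as the block size cannot be one, because 12 slots cannot hold 16 conditions equally. The Phase 1 aim names neither the combinations nor the means of getting them to each site, and section 4.3 could be taken to say that the same procedure serves both phases.

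If the statements reflected a real fault in the allocation, three things would be at stake: the balance of the factorial in Phase 2, the reproducibility of the randomization, and the chance that a site finishes its ten pilot participants without delivering a combination the team wanted to try there.

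**Working it through.** **1. Totals in Table 3.** Phase 2: 16 cells x 12 = 192, the planned enrolment. Phase 1: 12 x 1 + 4 x 2 = 20. Both reproduce.

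**2. The block label.** 12/16 = 0.75, so 12 is not a possible equal-allocation block length. It is 192/16, the number of replicates per cell, as the parenthesis in the same sentence says. Two structures fit: one list of 192, or 12 blocks of 16. Each ends with 12 per cell at full enrolment.

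**3. Effect on power.** Section 9.2 uses 192 - 34 = 158 analysed, and section 9.6 compares N/2 = 79 with 79 for every effect. Taking a two-sided level of .10, power = Φ(d√(79/2) - 1.645):

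- d = .40: Φ(2.514 - 1.645) = .808
- d = .50: Φ(3.142 - 1.645) = .933

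These match the plan's statements of more than .80 and more than .90. Read literally, α/2 = .10 gives .891 and .969, which also satisfy them. Block length and strata do not enter the formula.

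**4. Site balance in Phase 2 without stratification.** Assume one list of 192 split 96/96. The number at one site with a given component on has mean 48 and SD √(96 x ½ x ½ x 96/191) = 3.5, with a 95% range of 41 to 55. Site is a covariate in the model (section 9.6), so imbalance of this size is adjusted for.

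**5. Phase 1 under one shared list.** Assume the 20 entries of Table 3 form a single random list split 10/10. There are C(20,10) = 184,756 splits, all enumerated.

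The counts with components 1 to 4 on are 11, 11, 12 and 11. The counts without are therefore 9, 9, 8 and 9. Since each is below 10, no site can miss a component.

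| Present at both sites | Splits | Share |
|---|---|---|
| Every component | 184,756 | 100% |
| All six pairs of components | 177,232 | 95.9% |
| All four three-component sets | 120,010 | 65.0% |
| Cell 16 (all four components) | 97,240 | 52.6% |
| All four doubled cells | 14,784 | 8.0% |

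The last row is 2⁴ x C(12,6) = 16 x 924 = 14,784. It matters only if the doubled cells are the key combinations, which the protocol does not say. Cell 14 also has three components on, yet is not doubled.

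**6. What securing the combinations would cost.** Consider a ten-slot list for each site: one copy of each doubled cell plus six of the twelve single cells. The division of single cells would be drawn from the 162 (of 924) that keep each component's count within 1 between sites. This guarantees every row of the table at 10 per site.

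Exact recursion gives the average best-guess success over ten slots for someone who knows the rule and has seen the site's earlier allocations. It is 25% with this scheme. With the shared list it is 13%. Section 6.2.3 has an unblinded research assistant at each site who both recruits and facilitates the components.

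The guarantee also fails below 10. With 8 enrolled at a site (an assumption), the site list delivers all four doubled cells there with probability C(6,4)/C(10,8) = 15/45 = .33.

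**The case for a change.** The strongest case for acting is that allocation is the step a reader must be able to reproduce. Two of the three points need no assumption: the text contradicts itself on strata, and 12 cannot be a block length. Phase 1 exists partly to show that components are randomized and delivered correctly at each site, and the smallest correction would cost only a few words.

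The textual points stand. The verification step looks like a sentence left over from a stratified design, and the label is wrong. But neither misleads anyone about what is allocated. The statistician builds the tables and loads them into REDCap before Phase 1 recruitment. With no stratum in the system, there is nothing for staff to enter wrongly. Rewording the block sentence as 12 replicates per cell would still not say which of the two structures was used, and that can be read from the tables. One difference does remain: if Phase 2 stopped short of 192, blocks of 16 would leave cells more even than one long list. Section 9.6 already expects slightly unequal cells, and its linear model handles them.

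The Phase 1 point is missing detail, not a demonstrated fault. Section 9.2.1 speaks of randomization tables in the plural and sets Phase 1 apart. It then doubles exactly four cells for two sites, which fits one copy per site at least as well as a shared list. The statement in section 4.3 that procedures are identical introduces eligibility, timing and equipment. Table 3 openly gives different counts by phase, so that statement cannot mean identical lists.

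**Conclusion.** No change to the plan follows. The stratification and block-size statements are clerical slips. Table 3 and the definition inside the sentence settle the allocation at 12 per cell and 192 in total, and correcting the words would leave the cell counts, sample size, power and conclusions as they are.

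The Phase 1 gap is one the team can fill when it builds the lists. Even under the least favourable reading, a single shared list, every component reaches both sites with certainty, and Table 4 sets its target on correct delivery of components. The 53% and 8% figures are correct arithmetic but conditional on that list, and the 8% also on reading the doubled cells as the key combinations. Constrained site lists would buy certainty on combinations that no target requires. The price is a rise in predictability from 13% to 25%, in a 20-person feasibility pilot where an unblinded assistant recruits. That is a debatable trade-off, and leaving it to the study team is reasonable.

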9.3 Definition of Populations

All data analysis will use the intent to treat population and use all available data. There is no per protocol analysis planned.

9.4 Interim Analyses and Stopping Rules

9.4.1 Interim Analysis

There are no interim or futility analyses planned.

Data analysis of Phase 1 data will occur during and immediately after data collection in Phase 1.

Data analysis of Phase 2 data will occur after data collection in Phase 2.

9.4.2 Stopping Rules

This study will be stopped prior to its completion if: (1) the intervention is associated with adverse effects that call into question the safety of the intervention; (2) difficulty in study recruitment or retention will significantly impact the ability to evaluate the study endpoints; (3) any new information becomes available during the trial that necessitates stopping the trial; or (4) other situations occur that might warrant stopping the trial.

9.5 Outcomes

9.5.1 Primary/Proximal Outcome

Phase 1 is a pilot study to assess feasibility. The primary aims and outcome assessments are shown in Table 4 below.

Table 4. Targets for Phase 1 Pilot Study.		
Feasibility Area	Method of assessment	Target at each site
Recruit participants	Number recruited per month	Recruit 10 participants in 4 months.

Train yoga teachers to fidelity	Teacher fidelity scale	Each teacher demonstrates >80% fidelity on final 3 classes rated.
Randomize participants to intervention components and correctly administer these components	Randomization errors; receipt of incorrect intervention components	No errors/ incorrect components received in 2 nd half of participants randomized.
Collect follow-up assessments	Percent of follow-up assessments collected (for M1, M2, and M3)	≥ 70% with sufficient data collected on dosage; ≥ 70% of other follow-up assessments collected, including chart reviews

The proximal outcome of Phase 2 is yoga dosage received. This will be calculated by adding total number of minutes per week in the study yoga class and total number of minutes per week in personal practice (or outside yoga classes). Research staff will take attendance at study yoga classes, and, in the event someone does not attend the entire yoga class, will record the number of minutes present in class. We will measure personal practice using the Weekly Personal practice Questionnaire.

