6.2.4 Follow-up Visits

For the purposes of targeting dates for an assessment, we will consider each month = 28 days (4 weeks exactly). For all follow-up assessments, research staff will make every effort to conduct the assessment within one week before or one week after the exact due date of the assessment. However, because all data can be analyzed with modern statistical methods regardless of whether it was collected inside that window, RAs will still collect data if possible even if it is later than that two-week window. We will record optimum date for the assessment (e.g., Enrollment + 84 days for M3 assessment) as well as the actual date of the assessment. Note that we will attempt to conduct follow-up visits in person, but if that is not possible, we will collect data via telephone and a REDCap link, or via telephone only (if participant does not have access to a computer/ smartphone, e.g., pre-randomization, or at M6 or M12 follow-up).

Phase 1 and Phase 2 Visits:

- Weekly for 12 weeks
 - Study classes/groups
 - Homework Questionnaire
 - Injuries due to yoga
 - CEQ (after initial class only)
 - Any other AEs reported to RAs
- Month 1
 - Any other AEs reported to RAs
 - TSK
 - Self-efficacy for exercise
 - Logistic Factors
 - BREQ-2
 - BPI
 - NRS
 - ASI
 - Penn Craving Scale
 - Payment: \$20
- Month 2
 - Any other AEs reported to RAs
 - TSK
 - Self-efficacy for exercise
 - Logistic Factors
 - BREQ-2
 - BPI
 - NRS
 - ASI

- Penn Craving Scale
- Payment: \$20
- Month 3 (Final evaluation for Phase 1)
 - Any other AEs reported to RAs
 - TRAQ
 - TSK
 - Self-efficacy for exercise
 - Logistic Factors
 - BREQ-2
 - BPI
 - NRS
 - WHOQOL-BREF
 - PROMIS® Depression Scale
 - PROMIS® Anxiety Scale
 - ASI
 - Penn Craving Scale
 - SAFTEE
 - Chart Review
 - Qualitative Exit Interview (Phase 1 only)
 - Payment: \$30

Phase 2 Visits Only:

- Month 6
 - Homework questionnaire
 - Any other AEs reported to RAs
 - TRAQ
 - BPI
 - NRS
 - WHOQOL-BREF
 - PROMIS® Depression Scale
 - PROMIS® Anxiety Scale
 - ASI
 - Penn Craving Scale
 - Chart Review
 - Payment: \$30
 -
- Month 12 (Final evaluation for Phase 2)
 - Homework questionnaire
 - Any other AEs reported to RAs
 - TRAQ
 - BPI
 - NRS
 - WHOQOL-BREF
 - PROMIS® Depression Scale
 - PROMIS® Anxiety Scale
 - ASI
 - Penn Craving Scale

- Chart Review
- Payment: \$40

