9.2 Sample Size and Randomization

In RCTs a conclusion is made regarding the effect of intervention based on rejecting the null hypothesis with Type I error $<$ some predefined α . In contrast, in an optimization trial, a decision is made to include or exclude specific components in an intervention that will be tested in a future RCT. In this scenario, Type II error may be as pernicious as Type I error. Therefore, based on recommendations of Collins ³⁰ this study will be powered with $\alpha/2 = .10$. Because intervention effects are uncorrelated (or nearly uncorrelated if the design is not perfectly balanced), the alpha will not be corrected for multiple comparisons and all effects have equal statistical power. Assuming approximately 17% attrition for our primary outcome of dosage, we estimated power for $n= 158$ (192-34). To estimate the minimum detectable effect size we assumed a small correlation ($r = .15$) between recruitment site and yoga attendance and used the FactorialPowerPlan ³¹ macro in R. The proposed design has sufficient power ($1 - \beta > .80$) to detect a standardized difference in means of .40 or larger. Power to detect a medium standardized effect ($d = .50$) is $> .90$.

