Once data collection is complete, we will convene a meeting (or conference call) to make decisions about which intervention components should be included in the final intervention package. Participants in this meeting will include:

1. MPIs and co-Is and consultant [name];
2. Selected NCCIH staff (e.g., PO); and
3. Selected yoga instructors

At this meeting we will review all data collected.

Step 1: For each intervention component, we will first review the main and 2nd order interaction effects from the factorial experiment on the primary outcome of number of yoga minutes per week. We assume data will be missing at random. Missing data will be addressed using multiple imputation by chained equations.³³ Because the goal is intervention optimization, retention of components will not be based on a single criterion. We will initially choose to include all components for which there is a main or sympathetic interaction effect with a) an effect size (SMD) of 0.40 (estimated, based on preliminary data, to be 31 mins of yoga per week) or greater favoring the component; OR b) $p < .10$ favoring the component OR c) if the estimated Bayes factor provides substantial or stronger evidence preferring the intervention hypothesis to the hypothesis of no treatment effect. (See below for more information on Bayes factor).

Special cases:

1. Of monetary incentives for class attendance, we will look specifically at class attendance. If monetary incentives increase class attendance, and do not decrease overall minutes of practice, we will choose to include.
2. 3rd and 4th order interactions may be tricky to interpret. We will look at them, but place priority on main effects and 2nd order interactions in making decisions.
3. It is possible that 2nd order interactions may be antagonistic where the combination of two or more components is less effective than would be expected based on the main effects alone. At the same time, there may be significant positive main effects for both components. In this case, we will examine graphical depictions of results in order to determine whether to include both of the two components in question.

Step 2: All components that pass Step 1 will then be examined in light of their feasibility and acceptability. Data that bear on feasibility and acceptability include:

1. Participants' responses to qualitative interviews
2. Yoga instructors' experiences (field notes)

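### Does the undefined word sufficient in the Phase 1 dosage-data target (Table 4) make the target unusable or undermine the 17% attrition in section 9.2?

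*Combined protocol and SAP*

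**What the plan says.** Section 9.5.1 makes Phase 1 a feasibility pilot with targets per site in Table 4. For follow-up data, the method of assessment is "Percent of follow-up assessments collected (for M1, M2, and M3"), and the target has two halves: "≥ 70% with sufficient data collected on dosage" and "≥ 70% of other follow-up assessments collected, including chart reviews".

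The same section defines the Phase 2 outcome, yoga dosage, as "adding total number of minutes per week in the study yoga class and total number of minutes per week in personal practice" (outside classes count as practice). Class minutes come from attendance taken by staff. For the rest, "We will measure personal practice using the Weekly Personal practice Questionnaire". Section 6.2.4 lists a practice questionnaire, there called the Homework Questionnaire, under "Weekly for 12 weeks" and again at months 6 and 12. It is not in the visit lists for months 1, 2 and 3.

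Section 9.2 sizes Phase 2 thus: "Assuming approximately 17% attrition for our primary outcome of dosage", 192 - 34 = 158 participants. Section 9.3 commits to intention to treat with all available data. Section 9.6, Step 1, adds: "Missing data will be addressed using multiple imputation by chained equations".

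**The concern.** A target should be scorable by someone who has only the protocol and the data. Here the word sufficient has no threshold, and the percentage has no noun after it. Participants, participant-weeks and monthly blocks all look possible. The method column seems to make this worse, because the month 1, 2 and 3 visit lists in section 6.2.4 contain no dosage measure.

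Section 9.6 refers the Phase 1 analysis back to section 9.5.1, so no later text supplies the rule. Section 9.4.1 has Phase 1 data analysed during and straight after collection, so the rule could be chosen with results in view. If so, a site could be reported as passing or failing on the choice of definition alone. The pilot would then say little about the attrition assumed for Phase 2, where section 9.2 also does not say how many missing weeks make a participant lost. The outcome affected is the one that decides which components are kept.

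**Working it through.** **1. The plan's own figure.** Inputs from section 9.2: 192 randomised, 34 lost, 158 left, so 79 per level of each component (section 9.6 also gives 79). Alpha is taken as two-sided .10, in line with the p < .10 rule in section 9.6.

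- Power ≈ Φ(d·√(79/2) - 1.645).
- d = .40: Φ(2.514 - 1.645) = 0.808. The plan says above .80.
- d = .50: Φ(3.142 - 1.645) = 0.933. The plan says above .90.
- Loss: 34/192 = 17.7%, consistent with approximately 17%.

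The stated power stands whatever sufficient means in Table 4.

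**2. How far the missing threshold can move a pilot score.** One site has 10 participants × 12 weeks = 120 reports. Suppose 4 participants return 12 and 6 return 6 (a constructed split): 4×12 + 6×6 = 84.

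| Rule | Score |
|---|---|
| By report | 84/120 = 70% |
| Participants with at least 8 of 12 | 4/10 = 40% |
| Participants with at least 6 of 12 | 10/10 = 100% |

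Now assume each weekly report is returned with probability .70. The expected share of participants reaching the threshold is:

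| Threshold | Weeks independent (binomial) | Within-person correlation .3 (beta-binomial) |
|---|---|---|
| at least 6 | 96% | 79% |
| at least 8 | 72% | 65% |
| at least 10 | 25% | 47% |

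Neither the return rate nor the correlation comes from the documents. The tables show that the definition matters to the score. They do not show that any planned result is wrong.

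**3. Is the unit really open?** The second half of the target counts assessments and says so. The first half speaks of having sufficient data, which most naturally describes people. Section 9.2 also counts people. On the time frame, Table 1 in section 6.1 places the Homework Questionnaire in a weekly column headed with months M1, M2 and M3, the same three labels as in Table 4. Read as months, the method column covers the 12 weekly reports, and the apparent mismatch with the visit lists largely goes. This takes the Homework Questionnaire and the Weekly Personal practice Questionnaire to be one instrument. What remains open is the number of weeks.

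**4. Could the pilot check the 17% if the rule were written?** Exact 95% intervals: 7/10 gives 35% to 93%; 14/20 over both sites gives 46% to 88%. Both contain 158/192 = 82%. A site exactly on target, or both sites pooled, cannot separate 70% from the planning figure. Sections 1.1 and 3 give Phase 1 the job of documenting feasibility, not of estimating attrition.

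**5. What depends on the answer.** Table 4 attaches no progression rule to the 70%, and the stopping rules in section 9.4.2 do not refer to it. In Phase 2, sections 9.3 and 9.6 keep every randomised participant, with whatever weeks were reported and the rest imputed.

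**The case for a change.** The strongest reply is that the cure is almost free: a few sentences would fix the rule before data are seen, and a definition chosen afterwards is worth less. On the participant reading there is also a real comparison to make. A site passes with 30% of its participants lacking sufficient data, against about 17% planned. If 30% were lost in Phase 2, 192 × 0.70 ≈ 134 would remain (67 per level), and power at d = .40 would be Φ(2.315 - 1.645) = 0.749, below the stated .80.

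Part of this stands. The threshold is missing, and naming it in advance would be tidier. The power figure does not carry over: 70% is a floor for a pilot, not the Phase 2 assumption, and 0.749 is a complete-case calculation that gives no credit to partial data.

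The fuller remedy has costs. Any cut-off, such as 8 of 12, is a judgement without support in the documents. If the 17% were tied to it, a participant with 7 reports would count as lost in section 9.2 yet still contribute seven observed weeks under section 9.3. Prescribing imputation week by week would need an argument that it suits 12 weekly variables in 192 people better than the alternatives. That is a separate and ordinary analysis detail.

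**Conclusion.** No change to the plan is needed. Table 4 leaves out a detail that the analysts can supply sensibly: score participants at each site over the 12 weeks, and show completeness at several thresholds, since every weekly report is retained. The choice can swing a pilot percentage widely (40% to 100% in the constructed example), but it alters no stated figure, triggers no decision rule and excludes nobody from the Phase 2 analysis. The 17% in section 9.2 can be set beside the 70% once participants are taken as the unit, though samples of 10 and 20 make that comparison weak in any case.

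This rests on three readings: that the target counts participants, that M1 to M3 in Table 4 means the months heading the weekly column of Table 1, and that the two questionnaire names refer to one instrument. If the 70% were later made a formal condition for starting Phase 2, the threshold would have to be fixed first. The documents set no such condition.
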